Albuterol a β 2-adrenoreceptor agonist was first marketed in 1968 known for its bronchodilatory action. Albuterol contains a racemic mixture of two enantiomers namely the R(active form) and the L(considered inert) form. Some of the side effects of the racemic albuterol include jitteriness, anxiety and palpitations. Levalbuterol contains the single enantiomer (R – form) and is preferred in instances where the tachycardia caused by the racemate may be detrimental to the overall clinical status of the patient. However there are no studies to date that have elucidated the potential cause of the tachycardia in patients receiving albuterol attributed mainly to its β 2 receptor agonist function.

Field et al¹ measured the cost of breathing in 13 patients on mechanical ventilation as the difference between the oxygen consumption during spontaneous respiration and that during mechanical ventilation and found that the oxygen cost of breathing increases from less than 5 % of total VO₂ (oxygen consumption) in a normal resting spontaneously breathing patient to a range of 8 -24 % of total VO₂ on mechanical ventilation. Patients with cardiorespiratory or lung diseases have been shown to have elevated oxygen consumption while mechanically ventilated. β agonists can increase the oxygen consumption either by increasing minute ventilation through stimulation of the respiratory center or by directly stimulating the respiratory muscles. Furthermore there are no studies that have measured the change in oxygen consumption following administration of levalbuterol. Oxygen consumption increases in diseases states such as fever, sepsis and trauma and leads to an increased metabolic demand. Increase in oxygen consumption that is disparate to the oxygen delivery leads to anaerobic metabolism and lactic acidosis and can further worsen the clinical status or delay recovery. Also there may be impaired oxygen extraction or use at the cellular level i.e. cytopathic hypoxia thus creating a functional arteriovenous shunt. Maintaining adequate oxygen delivery to meet the metabolic demands is fundamental in treating critically ill patients.

A double blind placebo controlled trial studied pharmacokinetics of albuterol and its enantiomers and showed that, in fact the S enantiomer does not have any effects on extra pulmonary β 2 receptors. However the S enantiomer does not exert its effects through the β 2 receptor. Henderson et al² studied the clinical effects of the two enantiomers on mouse models and showed that the R enantiomer of albuterol increases airway edema and bronchial responsiveness in response to a methacholine challenge which provokes bronchoconstriction whereas the S enantiomer had the opposite effects. These bronchoconstrictor and proinflammatory effects of the S enantiomer may gradually overcome the bronchodilatory effects of the R enantiomer in the racemate and that R enantiomer balances the bronchospastic effects of the S enantiomer in the racemate. There are studies suggesting the differential effects of the two enantiomers.

[name] et al³ in 1990 reported changes in minute ventilation and oxygen consumption in 10 anesthetized intubated rhesus monkeys in response to multiple β agonists. The study revealed that of the multiple β agonists (salmeterol, formoterol, fenoterol, salbutamol) along with comparison to normal saline and theophylline, the most profound effects on oxygen consumption were after administration of inhaled racemic albuterol. Racemic albuterol increased the oxygen consumption (VO₂) by 46.5% over control (P < 0.001). Other variables such as heart rate, respiratory rate and minute ventilation also showed an increase of 60.2 %, 51.9% and 82.8% respectively. As the article stated, in patients with cardiorespiratory disease and with low reserve, the potential for hypoxemia will depend on the change in oxygen extraction and pulmonary vasculature and whether the cardiac

output can be increased to match the demand and if the extent of bronchodilation can increase ventilation to a degree that can sufficiently offset the increase in oxygen consumption.

In a follow up study by [name] et al⁴ in 1997 studied the effects of Bronchodilators on Spontaneous Ventilation and Oxygen Consumption in anesthetized intubated Rhesus Monkeys showed that racemic albuterol caused an increase in Oxygen consumption of 45% and minute ventilation of 50%. These changes were suppressed in the presence of a β blocker such as propranolol. Therefore the increase in oxygen consumption could be secondary to β adrenoreceptor stimulation resulting in stimulation of the respiratory center or due to increased metabolic demands.

β agonists are used extensively in pediatric patients with chronic lung disease, asthma or for its mucolytic property. Many of these children are admitted primarily for another condition for example septic shock, in which case their oxygen demands may already be increased. In such conditions administering β agonists that may further increase oxygen consumption and oxygen costs of the body may have deleterious effects on the overall clinical status of the patient.

C. Hypothesis: Levalbuterol does not increase oxygen consumption to an extent that is increased by salbutamol (albuterol).

D. Purpose of this Study: The purpose of our study is to study the peak oxygen consumption in subjects scheduled to receive albuterol and compare it with that of levalbuterol using a non-invasive method with the Innovision Innocor machine. To date, no known human studies that have measured the change in oxygen consumption after levalbuterol.

1. Study Objectives

Primary objective is to measure the peak oxygen consumption at baseline and then after the administration of albuterol and levalbuterol inhalation in patients admitted to or currently cared for in the pediatric intensive care unit (PICU) or cardiothoracic intensive care unit (CTICU) at Children's Hospital Los Angeles with asthma reactive airway or chronic lung disease.

Secondary objectives are to collect change in Cardiac output, systemic vascular resistance, stroke volume, minute ventilation, heart rate, blood pressure, respiratory rate, pulse oximetry with each intervention.

E. Significance and preliminary studies

Albuterol has been in used in the treatment of asthma to relieve bronchospasm for nearly 45 years. However numerous reports have associated long term use of racemic albuterol with increasing morbidity and mortality. Mechanisms underlying these observations are not well known at this point.

Recent studies have shown that the S enantiomer has bronchoconstricting and pro-inflammatory properties which may be counterbalanced by the R enantiomer in the racemate. Numerous studies have been reported to question the clinical efficacy of racemic albuterol or in fact that the racemate may actually have deleterious effects on the bronchioles. Racemic albuterol consists of 50% each of the active and the inactive isoform. However there is accumulating body of data from animal studies questioning the inactive or rather the counteractive nature of the S isoform.

Although β 2 agonists have been in use for a long time, controversies exist as to their efficacy and safety over long term use. Animal studies focusing on the long term use of racemic albuterol have shown that it increased airway hyper responsiveness, edema and susceptibility to spasmogens. These effects have been understood to be from the S isoform as previous clinical trials have demonstrated the individual bronchodilator properties of the R isoform along with suppression of pro inflammatory mediators.

Mazzoni et al⁵ have reported that bronchospasm in sensitized animals was completely suppressed by an infusion of racemic albuterol, however a more prolonged infusion longer than 1 hour increased their susceptibility to the antigen and induced hyper responsiveness to histamine. This progressive loss of efficacy of racemic albuterol with time is speculated to be from disproportionate accumulation of the S enantiomer due to stereospecific metabolism of the R enantiomer.

A randomized controlled trial was conducted by Wraight et al⁶ to study the adverse effects on lung function by short acting β agonists. The study included 36 subjects with mild to moderate asthma on racemic albuterol along with inhaled corticosteroids. Subjects were randomized to two groups, one receiving a combination of albuterol and ipratropium and the other receiving ipratropium alone. The study consisted of two phases. FEV1 measurements were done while on these medications during phase 1 and inhaled corticosteroids were then withdrawn during phase 2 and changes in FEV 1 and FEV1 % were recorded following the withdrawal. The results showed that there was a significant loss in lung function as evidenced by drop in FEV 1 in patients with mild to moderate asthma as compared to those on ipratropium. Furthermore when inhaled corticosteroids were discontinued there was a larger fall in FEV 1 in the β agonist group compared with the ipratropium group. These data suggest that in poorly controlled asthma wherein patients are taking short acting agonists frequently the adverse effects may be more pronounced especially when the anti-inflammatory effects of the inhaled corticosteroids are absent.

F. Research Design and Methods

Study Overview

This is a single center prospective randomized controlled open label cross over study in the 24 bed multidisciplinary medical-surgical Pediatric Intensive Care Unit (PICU) and 22 bed multidisciplinary Cardio-Thoracic Intensive Care Unit (CTICU) at Children's Hospital Los Angeles.

a. Eligibility & Recruitment

This will be a single center prospective randomized open label cross over study. There will be three cohorts of subjects.

1. Intubated patients receiving Albuterol
2. Non-intubated patients receiving albuterol who are cognitively able to obtain measurements with a mouthpiece
3. Healthy adult volunteers

a. Subject Eligibility – Intubated and non-intubated patients

For intubated patients all subjects 1 month to 17 years of age admitted to the pediatric intensive care unit (PICU) or cardiothoracic intensive care unit (CTICU) will be screened throughout their stay for inclusion. For non-intubated patients all subjects 1 month to 21 years old admitted to the pediatric intensive care unit (PICU) or cardiothoracic intensive care unit (CTICU) will be screened throughout their stay for inclusion. Particular subject eligibility will be based on the following inclusion and exclusion criteria.

b. Inclusion Criteria

For intubated patients: any patient 1 month to 17 years old admitted to the pediatric intensive care unit (PICU) or cardiothoracic intensive care unit (CTICU) with asthma, reactive airways or chronic lung disease and is scheduled to receive albuterol or levalbuterol.

For non-intubated patients: any patient 1 month to 21 years old admitted to the pediatric intensive care unit (PICU) or cardiothoracic intensive care unit (CTICU) with asthma, reactive airways or chronic lung disease and is scheduled to receive albuterol or levalbuterol.

c. Exclusion Criteria

1. If intubated, patients with a large endotracheal tube leak (greater than 18%)
2. SpO₂ less than 95 % while receiving an FiO₂ of > 40%, signifying intrapulmonary shunting in which case the use of albuterol or L-albuterol could change the degree of intrapulmonary shunt during the testing.

a. Subject Eligibility – Healthy Volunteers

Healthy volunteers less than 60 years of age available to participate on two consecutive days

b. Inclusion Criteria – Healthy volunteers less than 60 years of age

c. Exclusion Criteria – Any contraindication to use of Albuterol such as known allergy to albuterol or levalbuterol.

Protocol for intubated and non-intubated patients receiving albuterol or levalbuterol

After obtaining a written informed consent from patients/guardians that are scheduled to receive albuterol or levalbuterol, the subjects will be randomized using pre-prepared opaque sealed envelopes to two different groups, group A and B. The measurements will be done over 2 separate days. On Day 1 Group A will receive albuterol first followed by levalbuterol for when the next dose is due. On day 2 the order will be reversed and therefore levalbuterol will be given first followed by albuterol. Group B will be first given levalbuterol followed by albuterol for the next scheduled dose. If the patient is receiving albuterol as their clinically prescribed medication the levalbuterol dose will be chosen to be ½ that milligram amount. If the patient is receiving levalbuterol as their clinically prescribed medication the albuterol dose will be chosen to be 2 times that milligram amount. Typical dosages in the ICU would be albuterol 0.15 mg/kg with a minimum of 2.5 mg and maximum of 5 mg and levalbuterol 0.63 mg and 1.25 mg respectively. However, if a young child is clinically prescribed a dose of Albuterol of 1.25 mg(max dose of levalbuterol) then the dose of Levalbuterol for the study would be 0.63 mg. Albuterol is only FDA approved for marketing to patients greater than 2 years of age but it has been used clinically at all age levels. Likewise, Levalbuterol has been used clinically in infants and children but is only FDA approved for marketing to patients greater than 6 years of age. Measurements of oxygen consumption will be done using the non-invasive device Innocor. This device has been validated for measurement of oxygen consumption against the gold standard Douglas bag. Oxygen consumption will be measured at baseline and then after giving albuterol and levalbuterol at times 0, 5 min, 10, 20, 40 and 60 minutes. The two medications will be given at least 4 hours apart.

The Innocor device has the ability to measure cardiac output by mixing in small amounts of Nitrous Oxide (N₂O) and Sulfur Hexafluoride 6 (SF₆). Oxygen consumption is measured by the Innocor device without the addition of these gases. For this study N₂O and SF₆ will not be used. No part of the Innocor device will be attached to the skin for the purposes of this research. The Innocor device can be used to measure pulmonary function tests requiring some degree of cooperation from subjects. It is possible to obtain measurements of oxygen consumption using the Innocor device in intubated, sedated patients without their cooperation. For non-intubated patients, they would only need to be able to follow the direction to breathe out through the sensor. No timing of breaths are required.

Protocol for Healthy Adult Volunteers

After obtaining a written informed consent from the volunteer, the subject will be randomized using pre-prepared opaque sealed envelopes to which medication (albuterol or levalbuterol) they receive first. The measurements will be obtained over 2 consecutive days. The dosage of

Albuterol will be 5 mg mixed with 2 to 3 ml of saline and will be aerosolized over 10 minutes. The dosage of levalbuterol will be 1.25 mg mixed with 2 to 3 ml of saline and will be aerosolized over 10 minutes. On day 1 of the study the patient will receive the medication they were randomized to. At approximately the same time of day on day 2 the subject will receive the other medication. Following each breathing treatment, oxygen consumption will be measured using the non-invasive Innocor machine. Oxygen consumption will be measured at baseline and then following the medication at times 0, 5 min, 10, 20, 40 and 60 minutes. Temperature will be measured prior to the aerosolized medication and heart rate, blood pressure, oxygen saturations, and respiratory rate will be measured at intervals over the 60 minutes of oxygen consumption measurement.

The Innocor device has the ability to measure cardiac output by mixing in small amounts of Nitrous Oxide (N₂O) and Sulfur Hexafluoride 6 (SF₆). Oxygen consumption is measured by the Innocor device without the addition of these gases. For this study N₂O and SF₆ will not be used. No part of the Innocor device will be attached to the skin for the purposes of this research. The Innocor device can be used to measure pulmonary function tests requiring some degree of cooperation from subjects. For non-intubated patients, they would only need to be able to follow the direction to breathe out through the sensor. No timing of breaths are required.

$VO_2 = (CO \times CA) - (CO \times CV)$
VO₂ = Oxygen consumption
CO = Cardiac Output
CA = Oxygen concentration of arterial blood
CV = Oxygen concentration of mixed venous blood

Innocor is a non-invasive device that measures hemodynamic and gas exchange parameters for diagnostic purposes using the inert gas rebreathing technique and breath-by-breath analysis. The patient breaths through a mouthpiece or a facemask connected to the flow meter via a bacterial filter. A gas sampling tube is connected to the breathing assembly for side stream gas analysis. Carbon dioxide is measured continuously and simultaneously at the mouthpiece by a photoacoustic gas analyzer. Oxygen is measured by means of a laser diode absorption spectrometer.

The breath-by-breath method is the fastest responding of the non-invasive gas exchange methods for determination of the various gas exchange parameters such as oxygen uptake and carbon dioxide excretion. The Breath-by-Breath (BBB) Option provides measurements of metabolic gas exchange parameters by simultaneous measurements of the respiratory flow and gas concentrations when breathing ambient air. The respiratory flow is measured by means of a differential pressure type flow meter (pneumotachometer) placed between the respiratory valve unit and the patient. The principle in the determination of the oxygen consumption and the carbon dioxide excretion is to estimate the difference between airway influx and efflux of oxygen and carbon dioxide during inspiration and expiration. This is done by integrating the product of oxygen or carbon dioxide concentration and flow in the respiratory gas over an interval, which covers a complete respiratory cycle.

The gold standard for measuring respiratory exchange is the Douglas bag technique. Sheth et al⁷ studied the correlation of VO₂ obtained by Innocor with the Douglas bag technique. 31 children (ages 7 -17 years) were recruited for the study. A strong correlation was found between the two methods (R 2 0.82). The average discrepancy between the Innocor and the Douglas bag methods was 5.4% (range 0.1 – 32.2%). The Innocor provides a rapid mode of testing VO₂ as compared to the gold standard Douglas bag that involves collecting large volumes of expired gas as opposed to the Innocor where measurements could be completed in 60 seconds.

Measurements of cardiac output, stroke volume, systemic vascular resistance will be done using the Ultrasound Cardiac Output Monitor. We intend to collect data for such as cardiac output, blood pressure, systemic vascular resistance. These will be done with a non-invasive method using the Ultrasonic Cardiac Output Monitor (USCOM). USCOM device is FDA approved for use in adults and pediatric patients and includes a screen and a probe. The Ultrasonic Cardiac Output Monitor was introduced for clinical use in 2001 and measures the velocity of blood flow from either the aortic or pulmonary valve. It has previously been used in studies to measure cardiac output(CCI-09-00102) Cardiac output is the amount of blood pumped by the heart per minute expressed in litres. Cardiac output is a product of heart rate and stroke volume. Blood pressure will be entered manually by which the machine will calculate mean arterial pressure (MAP) and systemic vascular resistance (SVR). $SVR = MAP/CO$. Knowing changes in cardiac output with the interventions will provide vital information about the critical nature of their illness and this information can be used to tailor therapy for the patients. Our study entails measuring oxygen consumption. One of the fundamental tenets of critical care medicine include matching oxygen delivery to the oxygen consumption. Oxygen consumption that is disparate to the oxygen delivery leads to anaerobic metabolism and may explain the lactic acidosis seen in patients receiving albuterol. Oxygen delivery is the product of arterial oxygen content and cardiac output.

Study participants will be given a questionnaire at the end of each intervention. Oxygen consumption is dependent on many variables such as body temperature, amount of physical activity, amount of caffeine consumed and if they experience any effects such as nausea, palpitations, tremors or jitteriness. Collecting additional information for these confounders will be crucial in analyzing the final outcomes on the two groups with regards to change in oxygen consumption from baseline. The volunteers will also be asked if they have used albuterol or levalbuterol in the past. Albuterol is known to cause various effects such as nausea, palpitations, and tremors or jitteriness and knowledge about these side effects will help the physicians choose the most appropriate treatment for the subject.

G. Statistical considerations

There is no published information on the increase in oxygen consumption caused by L-Albuterol in humans. Animal studies show oxygen consumption increases from a baseline of 4.8 ± 0.3 ml/kg/min ([name] 1991) to 7.0 ± 0.3 ml/kg/min following L-Albuterol administration. This was an increase in oxygen consumption of 46%. Unpublished pilot data in rhesus monkeys suggests oxygen consumption increases from a baseline of 5.0 ± 0.6 ml/kg/min to 5.26 ± 0.8 ml/kg/min. However, differences in

sedation compared to previous animal studies resulted in greater variability in the measurement of oxygen consumption. We expect racemic albuterol will be associated with a smaller increase in oxygen consumption compared to L-Albuterol. A clinically significant difference in oxygen consumption might be as little as 10% in a child who is critically ill. We will use a paired t-test to compare mean difference in oxygen consumption between L-Albuterol and racemic albuterol in children. Using a paired difference to be detected of 10%, expected standard deviation of 20%, power of 0.9 and significance level (alpha) of 0.05 we calculated a sample size of 44 patients for this study. Given the possibility of drop out or incomplete data collection we anticipate approaching 50 patients to complete the study. Given we cannot be certain that the degree of variability will remain the same across the three cohorts we will target recruitment to 50 subjects in each cohort. We will perform an interim analysis after the first 20 patients are recruited.

References:

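### The crossover is open label with no reason given, so awake participants report symptoms knowing the drug, although masking the volunteers looks cheap

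*Combined protocol and SAP*

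**What the plan says.** Section F states the design twice. The Study Overview says "This is a single center prospective randomized controlled open label cross over study", and Eligibility & Recruitment repeats it: "This will be a single center prospective randomized open label cross over study". Nothing in the documents masks the participant, the person running the devices or the analyst, and nothing explains why masking was not used.

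For volunteers, the Protocol for Healthy Adult Volunteers describes the two preparations in matching terms: "Albuterol will be 5 mg mixed with 2 to 3 ml of saline and will be aerosolized over 10 minutes" and "The dosage of levalbuterol will be 1.25 mg mixed with 2 to 3 ml of saline and will be aerosolized over 10 minutes". The envelopes in that section fix the order only: "the subject will be randomized using pre-prepared opaque sealed envelopes to which medication (albuterol or levalbuterol) they receive first". They conceal the sequence before assignment and do not hide the drug afterwards.

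The questionnaire paragraph at the end of section F says "Study participants will be given a questionnaire at the end of each intervention". It asks about nausea, palpitations, tremor and jitteriness, and it gives the answers two uses. They serve as confounder information when the change in VO2 is analysed. They also have a prescribing purpose: "knowledge about these side effects will help the physicians choose the most appropriate treatment for the subject". The opening background has already told the reader what to expect of one drug: "Some of the side effects of the racemic albuterol include jitteriness, anxiety and palpitations".

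**The concern.** In a crossover each participant is compared with himself or herself, so anything that travels with the drug enters the within-subject difference directly. Expectation does this when the drug is known. Randomising the order protects against period effects but not against an effect tied to drug identity.

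The self-reported symptoms are the most exposed. They are subjective, they are collected straight after each known drug, and they are the effects that the background attributes to racemic albuterol. If they are then used to guide prescribing or to adjust the VO2 comparison, a reporting bias is carried forward. Heart rate, respiratory rate and VO2 in awake participants could also shift with anxiety or restlessness. The questionnaire paragraph itself says that VO2 depends on physical activity.

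**Working it through.** **1. Why the crossover does not cancel the bias.** Let δ be the true albuterol-minus-levalbuterol difference, b an expectation effect tied to drug identity, and π the change from first to second period.

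- Albuterol first: expected difference = δ + b − π.
- Levalbuterol first: expected difference = δ + b + π.
- Average over two equal sequences: δ + b.

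The period effect drops out and b does not.

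**2. Which measures are exposed, and in whom.**

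| Measure | Source | Exposure to participant expectation |
|---|---|---|
| Symptom questionnaire | End of section F | Direct, in awake participants |
| Heart rate, respiratory rate | Study Objectives; volunteer protocol | Possible, in awake participants |
| VO2 at baseline and at 0, 5, 10, 20, 40 and 60 min | Patient and volunteer protocols | Lesser: instrument-read, at discrete times |
| Any measure in sedated, intubated patients | Patient protocol | Little or none |

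For the person taking the measurements, the documents show one manual step. Blood pressure is typed into the USCOM, which derives mean arterial pressure and systemic vascular resistance from it.

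**3. Direction for VO2.** Section C hypothesises that levalbuterol raises VO2 less than albuterol. Section G expects racemic albuterol to raise it less than L-Albuterol, a term that the exclusion criteria appear to use for levalbuterol. The two expectations are opposed, so no direction can be assigned to a bias in VO2.

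**4. The plan's own figure.** Section G gives a paired difference of 10%, SD 20%, power 0.9, alpha 0.05 and n = 44. The standardised difference is 10/20 = 0.5.

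- Normal approximation: ((1.9600 + 1.2816)/0.5)² = 42.03, so 43.
- Exact two-sided paired t: power 0.893 at n = 43 and 0.900 at n = 44.

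The stated 44 reproduces with a two-sided test (a one-sided test would need 36). Masking does not change it.

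**5. Illustration only.** The documents give no bias size, so the values of b below are assumptions. With no true difference and SD 20%, the planned test has noncentrality (b/20) × √n. Its rejection probability, nominally 0.05, becomes:

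| Assumed b (percentage points) | n = 44 | n = 50 |
|---|---|---|
| 1 | 0.06 | 0.06 |
| 2 | 0.10 | 0.11 |
| 3 | 0.16 | 0.18 |
| 5 | 0.37 | 0.41 |

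The table shows only that recruiting more participants does not dilute a systematic bias. It is not evidence that a bias of any of these sizes exists.

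**The case against.** Open label is a declared choice, and the primary variable is read by an instrument. The VO2 readings are brief: section F says an Innocor measurement could be completed in 60 seconds. The volunteer protocol does refer to 60 minutes of measurement, but the schedule is a set of discrete times. The primary objective concerns intensive-care patients, and those who are intubated and sedated have little route for expectation. Symptoms are not among the primary or secondary objectives, and no between-drug symptom test is specified. What participants are told about the drugs cannot be seen. All of this stands, and it limits the point to awake participants and mainly to the questionnaire.

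A reader might infer more in four ways, none of which the documents support:

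- **That any drug difference in VO2 could not be told apart from expectation.** This ignores the instrument reading, the short measurements and the sedated cohort.
- **That expectation must favour levalbuterol.** This holds at most for symptoms. For VO2 the plan contradicts itself.
- **That the USCOM results depend on how the probe is held, or that someone selects breaths.** The documents say only that the device has a screen and a probe, and that gas exchange is integrated over a complete respiratory cycle.
- **That full masking is already shown to be achievable.** Diluent range and delivery time match in volunteers only. Drug-solution volume and appearance are not given, the patient protocol gives no diluent volume or delivery time, and staffing is not described.

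The objection does not remove the core. The plan gives symptom answers both a prescribing and an analytic role, collects them with the drug known, and offers no reason for doing so when the volunteer preparations invite masking.

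**Conclusion.** The point holds as a design weakness with an inexpensive improvement, not as an internal error. Self-reported symptoms in awake participants can be biased by knowledge of the drug. Heart rate, respiratory rate and VO2 in the same participants can be biased to a lesser degree. The size cannot be estimated from the documents, and the direction for VO2 is unclear. Sedated, intubated patients are little affected. The conclusion assumes that awake participants hold some expectation about the two drugs. The background makes this plausible but does not demonstrate it.

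**What to change.** In the volunteer cohort, and in awake patients where feasible, replace open label with participant-masked, and add wording to this effect:

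> The nebuliser is prepared out of the participant's sight to the same total volume for both drugs. Sessions are labelled by number only. The drug is not disclosed to the participant until that participant's questionnaire and readings have been recorded. Where a different person already gives the dose, the person who runs the devices, enters blood pressure and gives the questionnaire is also kept unaware of the drug. Treating clinicians have access to drug identity at all times.

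Where masking is judged not feasible, the protocol should say why.

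The cost is some preparation and labelling effort. Doses, measurement times and sample size do not change. Masking the participant needs no extra staff. Masking the person who takes the measurements is asked for only where the tasks are already split, because the documents do not say who does what. Masking may be imperfect if the drug solutions differ in volume or appearance, so this should be checked before the wording is adopted.

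### Patients prescribed levalbuterol are assigned racemic albuterol with no check on why levalbuterol was chosen

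*Combined protocol and SAP*

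**What the plan says.** Section F gives separate eligibility lists for patients and for healthy volunteers, and states that "Particular subject eligibility will be based on the following inclusion and exclusion criteria".

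- **Patients, inclusion.** An intubated or non-intubated ICU patient with asthma, reactive airways or chronic lung disease qualifies if he or she "is scheduled to receive albuterol or levalbuterol". Either prescription is enough.
- **Patients, exclusion.** There are two items. The first begins "If intubated, patients with a large endotracheal tube leak (greater than 18" and gives that figure as a percentage. The second is an SpO2 below 95% on an FiO2 above 40%, justified by possible changes in shunt.
- **Volunteers, exclusion.** There is one item: "Any contraindication to use of Albuterol such as known allergy to albuterol or levalbuterol".
- **Patient dosing.** In the patient protocol, each subject receives both drugs. For those already on levalbuterol the rule is: "If the patient is receiving levalbuterol as their clinically prescribed medication the albuterol dose will be chosen to be 2 times that milligram amount". No condition is attached.

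The background at the start of the protocol says that levalbuterol is the drug of preference where tachycardia from the racemate might do the patient harm.

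**The concern.** By the protocol's own account, a levalbuterol prescription can be a deliberate decision to keep a patient off the racemate. The inclusion criterion admits such a patient and the dosing rule assigns the racemate. Nothing visible in between asks whether that is acceptable.

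The contraindication and allergy line would be the natural place for part of this check, but it is written for volunteers only. Copying it across would not settle the matter by itself, because a prescriber's preference for levalbuterol is not a contraindication to albuterol.

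What is at stake is patient safety and respect for the treating clinician's judgement, in a population that includes a cardiothoracic ICU. No statistical quantity is at stake.

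**Working it through.** The plan attaches no figure to this point, so the check sets its provisions side by side.

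**1. What the patient exclusions screen for.** One item concerns tube leak and the other intrapulmonary shunt. Both bear on the measurement. Neither asks whether the patient can take either drug.

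**2. What the clinical order already covers.** Levalbuterol is the R form alone (background). Racemic albuterol is half R and half S (Section E). The study dose is half the milligrams when going from albuterol to levalbuterol, and twice when going the other way (patient protocol). Write A or L for the prescribed milligrams.

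| Prescribed | Other study drug | R in the prescribed dose | R in the other drug | New component |
|---|---|---|---|---|
| Albuterol A | Levalbuterol A/2 | A/2 | A/2 | None |
| Levalbuterol L | Albuterol 2L | L | 2L × 0.5 = L | S form |

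The order for albuterol therefore already accepts everything in the study levalbuterol dose. The order for levalbuterol does not accept the racemate. The comparison is of enantiomers only; the documents do not discuss formulation.

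**3. How often the racemate is given.** Group A receives albuterol on both days. Group B receives it on day 1, and its day 2 is not described. So every levalbuterol-prescribed patient who completes day 1 receives it at least once.

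**4. Whether any step intervenes.** Between the background statement about tachycardia and the doubling rule, the visible text has written consent and randomization by sealed envelope. It has no prescriber agreement, no question about the reason for levalbuterol, and no exclusion on that ground.

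**5. How many patients.** The documents give neither the share prescribed levalbuterol nor the reasons for those prescriptions. The possible range runs from none to all of the two patient cohorts, where "we will target recruitment to 50 subjects in each cohort". The cohort labels in Section F and the purpose in Section D speak of patients receiving albuterol, which suggests the lower part of that range.

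**6. Effect on the sample size.** Section G uses a paired difference of 10%, a standard deviation of 20%, power 0.9 and alpha 0.05. A two-sided paired t-test with these inputs needs n = 44 (power 0.900), which is the plan's figure. The change proposed here alters none of the four inputs.

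**The case against.** The case on the other side is substantial.

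- **Volunteers and patients differ for a reason.** Volunteers have no prescription, so the protocol must screen them itself. Every patient has a clinical order for one of the drugs. This stands for albuterol-prescribed patients, as step 2 shows. It does not reach the racemate in levalbuterol-prescribed patients.
- **The main population appears to be on albuterol.** The cohort labels support this. They do not displace the inclusion criterion or the dosing rule, both of which name levalbuterol expressly, as does the consent step: "After obtaining a written informed consent from patients/guardians that are scheduled to receive albuterol or levalbuterol".
- **The motive is inferred from one general sentence.** The background does not say why patients at this site receive levalbuterol. That is correct, and it is why a question to the prescriber is proposed rather than a blanket exclusion.
- **There are safeguards.** The study is open label, doses are given when clinically due, heart rate and blood pressure are collected, and a questionnaire asks about palpitations and tremor. These act during or after dosing, and no visible text ties them to a withdrawal rule. Consent pages are absent from the copy reviewed, so a check placed there cannot be ruled out.

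A reader might infer that the rule exposes these patients to demonstrated harm. The documents do not support that. The R dose is unchanged, the background says the cause of the tachycardia has not been elucidated, and it reports no S effect on beta-2 receptors outside the lung. The S effects described in Section E concern the airway, not heart rate.

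A reader might also take the doubling as an overdose. The typical ICU doses are given as albuterol "with a minimum of 2.5 mg and maximum of 5 mg and levalbuterol 0.63 mg and 1.25 mg respectively". Doubling those levalbuterol doses gives 2 × 0.63 = 1.26 mg and 2 × 1.25 = 2.5 mg of albuterol, at or below the bottom of the typical albuterol range.

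**Conclusion.** The point holds in a narrow form. The visible eligibility and dosing rules allow a patient prescribed levalbuterol to be given the racemate without anyone asking whether the prescriber meant to avoid it. The patient list also lacks the drug-suitability exclusion that volunteers have.

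It is tempting to read the missing line as leaving both patient cohorts unscreened and at risk. The documents do not support that: the clinical order already screens for the prescribed drug, and an albuterol-prescribed patient meets no new enantiomer on switching. The gap that matters is confined to levalbuterol-prescribed patients.

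Their number is unknown and may be small, and added harm is not demonstrated. The primary estimate and the sample size are unaffected. This is a cheap improvement in patient safety, for the sponsor to consider. It rests on two assumptions: that some levalbuterol prescriptions are made for the reason the background gives, and that no equivalent check sits in pages not available here.

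**What to change.** Make two changes to Section F.

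1. Before enrolling a patient prescribed levalbuterol, record the prescriber's agreement that racemic albuterol is acceptable, and exclude the patient if it is not. An example is levalbuterol chosen because tachycardia on the racemate was judged harmful for that patient. All other levalbuterol-prescribed patients remain eligible.
2. Extend the volunteers' contraindication and allergy exclusion to the patient list, covering both study drugs.

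Both are needed, because the second would not catch a preference that falls short of a contraindication. The work is one screening question and one added line. A few patients will be lost, and the results will not apply to those who cannot take the racemate, a group for whom the comparison is clinically relevant. The analysis and the recruitment targets stay as they are.
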